However, our current cohort (11 of 13) is in week 6 of the 8-week intervention. Thus, we plan to conduct these by phone conferencing using UMN Zoom. We will not use the video portion of Zoom because not all participants have access to the internet. We will conduct each meeting according to our intervention manual, which delineates topics for discussion and exercise per Otago protocol. Similar to in-person intervention meetings and when participants perform these exercises at home independently (2 times per week to every day), there is a small risk of discomfort or injury. Consistent with our protocol and the Otago Exercise Program manual we will minimize the risk using several strategies. First, the exercises in Otago are considered safe for older adults, including those with frailty and multiple chronic conditions. Second, we will ensure that all phone conference participants have water, and are near sturdy structures during the exercises, such as a non-rolling chair or a counter. Third, we will remind participants to stop exercising if they feel discomforts such as joint pain or shortness of breath. Finally, at this point in the intervention, all participants who will participate in the conference call have mastered the exercises and know how to personally adapt them according to ability, comfort, and preferences.

Table 3 highlights condition and content by time. Each contact is 90 minutes: 10 for questions and answers; 40 for Otago PA; 20 for interpersonal behavior change strategies; 20 for intrapersonal behavioral change strategies; and, in lieu of behavioral change strategies--20-40 for attention control topics related to Health & Age, based on the National Institute of Aging website, Health & Aging.⁶²

Table 3. Condition, Content, and Time

Time in Minutes	Condition and Content			
	Otago/PA	Otago/ PA + Inter-personal	Otago/ PA + Intra-personal	Otago/ PA + Inter-personal + Intra-personal
10	Q& A	Q&A	Q&A	Q&A
40	Otago	Otago	Otago	Otago
20	Health & Age	Inter-personal	Health & Age	Inter-personal
20	Health & Age	Health &Age	Intra-personal	Intra-personal

The social milieu in each small group meeting will support friendly and positive interactions and discussions guided by curricula topics and objectives. All content (experimental, attention control, core) is summarized in the next six paragraphs.

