Experimental component: Interpersonal content. In the interpersonal component, a dialogue between small group participants will be facilitated focusing on their knowledge and experiences integrating fall-reducing PA into their social routines, providing and receiving social support for exercise, and using relevant community resources. Non-competitive, friendly, social comparison and exchange will also be facilitated, focusing on sharing different ways to practice fall-reducing PA; PA patterns derived from personal PA-monitor data; what others think about PA; and sharing PA data with important others (e.g., family, friends, providers).

Experimental component: Intrapersonal content. The intrapersonal component discussions will focus on guiding participants to develop, and modify as needed, personally meaningful goals and plans, using the National Institute on Aging's Go4Life⁶³ goal- setting and weekly planning PA worksheets. Discussions will also address personal barriers management; habit formation; coping with potential setbacks; and self-monitoring PA outcomes, congruent with personal goals.

Attention control content: Health & Age. Similar to our preliminary research, we will provide attention control topics about Health & Age, from the National Institute of Aging website including information about falls, pain, nutritional supplements, sleep, hearing, memory, and vaccinations.

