Core content: Otago (PA protocol). The evidence-based Otago protocol guides the core fall-reducing PA content in this study. It is feasible and effective in community-dwelling older adults, including those with multiple chronic conditions (e.g., osteoporosis), pain, and frailty.^{10, 13, 64} Our team and others have successfully implemented the Otago PA protocol in small groups.^{13, 49} The overarching goal of Otago in this study is to facilitate participants' mastery and individualization of specific movements and exercises so they can self-direct their practice of these outside the small group setting. The program includes 5 flexibility movements (back extension and ankle, head, neck, trunk movements), 5 leg strengthening exercises (knee extensor, knee flexor, hip abductor, ankle plantar flexes, ankle dorsiflexes), 12 balance movements (knee bends, backwards walking, walking and turning, sideways walking, tandem stance, tandem walk, one leg stand, heel walking, toe walking, heel-toe walking backwards, sit to stand, stair walking), and a walking plan. The number, intensity and duration of movements are gradually increased.⁶⁵ Thus, time spent on the combined movements and exercises slowly increase across the 8-week intervention from approximately 15 to 35 minutes per meeting. We encourage participants to increase their walking time by 20% of their baseline average -up to 30 minutes per day. We also encourage participants to self-direct their practice of Otago PA that they have mastered, outside the small group meetings. Some choose to practice their leg-strengthening and balance PA during one timeframe. Others choose to practice different types of PA at different times of the day (e.g., balance exercises while waiting for coffee to brew, leg-strengthening exercises while watching TV). Similarly, some choose to take 30-minute walks once per day, others prefer to take break their walking time up into 10 minute bouts. In total, participants are encouraged to practice their personalized Otago PA protocol every other day (approximately 70 minutes per week) and to walk approximately 30 minutes per day (150 minutes per week), which is consistent national and international PA guideline recommendations for minimal PA among older adults, including those with multiple chronic conditions.⁵⁹ When participants cannot practice the amounts of PA recommended in Otago due to health conditions, they are encouraged to be as physically active as their abilities and conditions allow.^{59,66}

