5.1 STUDY DESIGN

Experimental. We will address this proposal's aims and hypotheses using a 2x2 factorial experiment where one factor represents receipt of an interpersonal intervention component (No vs Yes) and the second factor represents receipt of an intrapersonal intervention component (No vs Yes). Three hundred and eight community-dwelling older adults will be randomized to 1 of 4 conditions, which represent distinct combinations of experimental components (sets of interpersonal and intrapersonal behavior change strategies) and core intervention content (evidence based physical activity protocol and a physical activity monitor). The study will be implemented in 13 waves over 48 months, within Minneapolis and St. Paul community centers. Interventions for each condition will be delivered to small groups of participants (4-6) randomized to the same condition. These small groups will meet every week for approximately 90 minutes over the course of 8 weeks.

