We believe participation in this research will yield benefits for participants. Mastery of physical activities within the Otago PA protocol will provide participants with skills and knowledge to practice these exercises safely at home or in other environments of their choice. The behavioral change strategies in the intervention have the potential to motivate participants continued engagement in PA. Participants will also receive a PA-monitor for self-tracking and support to use it as well as interpret its data.

CHAPTER 17 – DATA MANAGEMENT

17.1: DATA ANALYSIS PLAN

Statistical analysis. Descriptive statistics (means, standard deviations, ranges for continuous variables and counts/ percentages for categorical variables) will be used to summarize biologic, demographic, outcome, and exploratory measures by treatment arm, actual and projected accrual, attendance and retention rates, quality control data (e.g., missing data), and fidelity data. Tables, graphs and charts will be used to visualize data when appropriate. Enrollment summaries will be reviewed at weekly research staff meetings throughout enrollment phases and every month during non-enrollment phases. Differences by randomly assigned condition will be assessed with one-way ANOVA tests for continuous and Fisher's exact test or chi-square tests for categorical variables as appropriate. Any identified confounders will be adjusted for in subsequent analyses. All analyses will be pre-planned and conducted while masked to condition.

We will include all cases in analyses, regardless of intervention attendance rates or attrition. Missing data will be analyzed. We anticipate, based on preliminary research that the rate of missing data will be low and similar across conditions, but that it may be associated with severe illness that leads to dropout or inability to capture follow- up PA data. Thus, similar to preliminary analyses, we will conduct a sensitivity analysis of complete cases and imputing worst case carried forward.

Primary Aim: Intervention component effects on PA will be assessed using 2x2 full factorial ANCOVA models with duration of total PA as the outcome (average minutes per

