week). The factors, or independent variables, are interpersonal and intrapersonal components; each with two levels indicating exposure (No vs Yes). Different models will be developed for PA measured objectively. PA will also be measured via self-report. Each model will include baseline PA values as a covariate. Main and interaction effects of the components on the duration of PA will be tested immediately, 6 months, and 12 months post- intervention. Further, we will apply multilevel longitudinal data analyses to examine the variation of component effects across time-points (baseline; immediately post-intervention; 6 months' post-intervention; and 12 months' post- intervention), including interactions between components (e.g. interpersonal x intrapersonal x time), which will allow us to see when an older adult might benefit from additional support to maintain PA.

Secondary Aim: The secondary outcome of Falls will first be described using the number of falls, fallers, fall rate, and time to first fall post-intervention.⁷⁴ Given the expected distribution of falls, we will use negative binomial regression models to estimate the between-group difference in fall rates 12 months' post-intervention. Quality of Life data will be assessed using 2x2 full factorial ANCOVA and longitudinal analyses described for Aim 1 with total mean QOL as the outcome variable.

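### Every condition is delivered in same-condition small groups of 4-6, but the PA, QOL and falls models name no group term, so the component tests are too liberal if outcomes correlate within group

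*Combined protocol and SAP*

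**What the plan says.** Section 5.1 describes individual randomization to one of four conditions, followed by group delivery: "Interventions for each condition will be delivered to small groups of participants (4-6) randomized to the same condition". Groups meet weekly for 8 weeks. The same section adds: "The study will be implemented in 13 waves over 48 months". Section 4.1 puts cohorts at 16 to 24 people in groups of 4 to 6.

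Section 17.1 sets the primary analysis: "Intervention component effects on PA will be assessed using 2x2 full factorial ANCOVA models with duration of total PA as the outcome". The terms are the two factors and their interaction, tested immediately, at 6 months and at 12 months, and "Each model will include baseline PA values as a covariate". Any confounders identified by comparing conditions are also adjusted for. QOL uses the same ANCOVA and longitudinal models. Falls use negative binomial regression. In addition, the plan proposes "multilevel longitudinal data analyses to examine the variation of component effects across time-points", without stating the levels.

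Section 17.2 bases 308 participants on a standardized effect of .20, 15% attrition at 12 months, 80% power and two-sided alpha of .05. It mentions neither an ICC nor a design effect.

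**The concern.** Everyone in a small group has the same level of both factors. The two main effects and the interaction are therefore contrasts between groups, even though people were randomized individually. Individual randomization balances participants at baseline; it does not keep outcomes independent after eight weeks of shared treatment.

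Within-group correlation is plausible. Section 4.1 plans for every group that "The social milieu in each small group meeting will support friendly and positive interactions", and in the interpersonal component "Non-competitive, friendly, social comparison and exchange will also be facilitated". Section 5.2 also measures group cohesion after the intervention. If such correlation exists, an ANCOVA without a group term counts group-to-group variation as participant-level information. The trial's purpose is to decide which component to keep, so the practical risk is keeping one that does nothing.

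**Working it through.** **Inputs.** Groups of 4-6 (section 5.1); 13 waves (section 5.1); 308 participants and 15% attrition (section 17.2). The number of groups is not stated, but 13 waves × 4 conditions implies about 52, with 308/52 = 5.9 per group and .85 × 5.9 = 5.0 analysed. The bounds used are m = .85 × 4 = 3.4 to .85 × 6 = 5.1. The ICC is an assumption, ranged over .01 to .10. It means the within-group correlation of the baseline-adjusted outcome.

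**The plan's own power figure.** The stated 80% is not reproduced. For a main effect with 262 analysed, independent data and 257 df, power is about 36% if .20 is a standardized mean difference *d*, and about 90% if it is Cohen's *f* (d = .40). This is a separate problem and adds no weight here.

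**True alpha of the nominal 5% PA or QOL ANCOVA test.** Let R be the true variance of a component contrast divided by the variance the ANCOVA assumes:

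- ICC in all four conditions: R = 1 + (m − 1)ICC
- only in the two interpersonal conditions: R = 1 + (m − 1)ICC/2
- half of it shared by the whole wave: R = 1 − ICC + m·ICC/2
- all of it shared by the wave: R = 1 − ICC

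Then alpha = 2[1 − Φ(1.96/√R)]. For example, at m = 5.1 and ICC .05, R = 1 + 4.1 × .05 = 1.205, which gives 7.4%.

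| ICC | All four | Interpersonal only | Half at wave level | All at wave level |
|---|---|---|---|---|
| .01 | 5.3-5.5% | 5.1-5.2% | 5.1-5.2% | 4.9% |
| .02 | 5.55-5.95% | 5.3-5.5% | 5.2-5.4% | 4.8% |
| .05 | 6.4-7.4% | 5.7-6.2% | 5.4-5.9% | 4.4% |
| .10 | 7.8-9.9% | 6.4-7.4% | 5.8-6.8% | 3.9% |

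These use 12-month attrition. With full groups of 4 to 6, the all-four case gives 6.8-8.0% at ICC .05 and 8.6-11.0% at .10, so inflation is somewhat larger at the earlier time-points.

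**Simulation check.** The plan's ANCOVA with 52 groups and 15% loss rejected 4.9, 5.7, 6.1, 7.6 and 10.0% at ICC 0, .01, .02, .05 and .10, in line with the formula. A 76-group layout with mostly groups of 4, taken as a bounding case, gave 5.0, 5.0, 5.4, 6.2 and 8.3%.

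**Falls.** Rates had to be assumed: .5 falls a year with dispersion 1, which gives 1 − 1/(1 + .5) = 1 in 3 fallers, the proportion in section 2.1; or 1.0 a year with dispersion 1.5. The negative binomial Wald tests of the two components and their interaction rejected 5.2-5.6% at ICC 0, then 5.6-6.3, 5.9-6.8, 7.3-8.9 and 9.4-12.1% at .01, .02, .05 and .10 on the count scale. With correlation only in the interpersonal conditions, the last four are 5.6-6.3, 5.7-6.4, 6.2-7.2 and 7.5-9.3%. The dispersion parameter does not absorb group correlation.

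**Power once groups are respected.** The noncentrality is d√262/2 divided by √R, with 36 df (m = 5.03) to 60 df (m = 3.4). At ICC .05 power is 30-32% (*d*) or 82-85% (*f*). At .10 it is 26-30% or 76-82%.

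**The case against.** The strongest reply is that material harm depends on an ICC that nobody has shown. Contact is only eight weekly meetings, and section 4.1 says "We also encourage participants to self-direct their practice of Otago PA that they have mastered, outside the small group meetings". Nothing shows that group influence lasts to 12 months. At an ICC of .01-.02 the inflation is small, and wave-level correlation causes none. All of this stands, and it limits the size of the problem. It does not remove it: the model is also tested immediately after the intervention, when group influence is most recent.

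A second reply is that *multilevel* may have been meant to include the small group. That is possible for the longitudinal models, where the fault is only under-specification. But those models are additional, are described over time-points, and do not reach the ANCOVAs or the falls model. Confounder adjustment does not help either: small group is nested in condition, so entering it as a fixed effect would absorb the component contrasts.

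Third, the sample size may contain an unreported allowance. Reading .20 as *f*, with groups of 5 and ICC about .08, gives 198 × 1.32/.85 = 307.5, close to 308. The documents neither say this nor exclude it. It would bear on power, not on the missing model term.

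Fourth, the falls figures rest on assumed rates, on factorial terms the falls plan does not spell out, and on a test that already rejects slightly above 5% at ICC 0. They are indicative only. Likewise, sections 4.1 and 5.1 point to about 52 groups, so the lower ends of the ranges describe a less likely layout.

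**Conclusion.** The concern holds. As written, the ANCOVAs for PA and QOL and the falls model treat participants as independent when both components and their interaction vary only between small groups. Any positive within-group correlation beyond wave then makes standard errors too small.

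For PA at 12 months the effect is minor at ICC .01-.02 (at most about 6%) and material at .05 or more (6.4-9.9% if all four conditions are affected, and less if only the interpersonal ones are or if part is shared by the wave). The omission is certain from the text; the size is conditional on an ICC the documents do not give. This should be fixed, but it does not invalidate the design.

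**What to change.** - **PA and QOL, ANCOVA and longitudinal models:** add a random intercept for the actual small group and wave as a fixed block, with Kenward-Roger or equivalent degrees of freedom. Use the actual group rather than wave × condition, in case a wave holds two groups of one condition. Where software allows, do not bound the group variance at zero. In simulation this model rejected 3.5-5.2% bounded and 4.4-5.6% unbounded. Dropping the wave block took rejection down to 1.7-2.3% when an ICC of .10 was all at wave level.
- **Falls:** use the same random intercept (not simulated here) or cluster-robust standard errors with a small-sample correction. A simple G/(G−1) correction, G being the number of groups, with t on G−4 df still gave 5.1-6.4%, so a stronger correction is preferable.
- **Group membership:** section 5.2 lets participants delay, rarely, to a later course of the same condition, but names no group for analysis. Pre-specify one, for example the course attended, with the original group as a sensitivity analysis. Keep never-attenders in their assigned group. Condition is unchanged, so intention to treat is preserved.
- **Reporting:** state the levels of the longitudinal model, report the ICC at each time-point, say whether .20 is *d* or *f*, and restate power over an ICC range such as 0 to .10.

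**Cost.** SAP wording, plus group and wave identifiers in the analysis file, which can be coded so analysts stay masked. The documents do not say that the group identifier is stored. Attendance is recorded after each meeting (section 5.2), so whether it can be recovered must be confirmed. No extra participants are needed. Intervals widen slightly: with zero ICC, at an effect where the plan's ANCOVA has 79% power, the mixed model had 77-78% unbounded and 74-76% bounded.

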Our research team will conduct a 2 x 2 factorial experiment testing the individual and combined effects of two empirically and theoretically relevant sets of behavior change strategies on community-dwelling older adults' physical activity. To do this we will randomize participants ≥ 70 years old ($n = 308$) to 1 of 4 experimental conditions. All conditions include an evidence-based physical activity protocol endorsed by Centers for Disease Control and Prevention (CDC) for use by all older adults, including those with frailty and multiple co-morbidities and the commercially available physical activity monitor (e.g., Fitbit) to augment intervention delivery. Intervention components that are experimental and vary by condition are the sets of behavior change strategies which will be combined with the physical activity protocol and the physical activity monitor. Condition 1 has no specific behavior change strategies; Condition 2 includes an intervention component comprised of 5 interpersonal behavior change strategies, such as facilitating social support and social comparison; Condition 3 includes an intervention component comprised of 5 intrapersonal behavior change strategies, such as setting personally meaningful goals; and Condition 4 includes both sets of behavior change strategies -- 5 interpersonal strategies combined with 5 intrapersonal behavior change strategies.

To fully examine the effects of these experimental components, we have delineated Primary, Secondary and Exploratory Aims:

Primary Aim: Determine which experimental intervention component(s) increase PA among community-dwelling older adults post-intervention: immediately, 6 months, and 12 months.

Hypothesis: Participants receiving the interpersonal set of behavior change strategies will have clinically meaningful increases in PA post- intervention (at all 3 time-points), compared to participants not receiving these strategies.

Secondary Aim: Determine which experimental intervention component(s) decrease fall occurrence and increase quality of life (QOL) among community-dwelling older adults 12 months post-intervention. **Hypotheses:** Participants receiving the set of interpersonal behavior change strategies will have clinically meaningful reductions in falls and increases in QOL, 12 months post-intervention, compared to participants not receiving these strategies.

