2.1 SIGNIFICANCE OF RESEARCH QUESTION/PURPOSE

A description of the relevant prior research and gaps in current knowledge for your research question.

Every year, 1 in 3 people aged 65 and older falls; 25% of which result in serious injury or death and have devastating effects on QOL.^{1,5} Despite evidence that PA targeting leg strength and balance reduce falls, less than 12% of older adults engage in these activities on a regular basis and fall rates continue to increase.⁷ Research examining intervention strategies that motivate older adults to engage in PA is scarce and inconclusive. There is a compelling need to identify specific behavioral change strategies that effectively and efficiently motivate older adults to sustain increased levels of PA.

Several behavioral change strategies have the potential to motivate older adults to engage in PA, such as facilitating social support;¹⁹ barriers management;²⁷ goal-setting;²⁸ habit formation;²⁹ and self-monitoring outcomes.³⁰ To date, intervention studies typically combine 7-10 strategies and evaluate them as part of an “intervention package” compared to a control group. Thus, it is not known which strategy, or set thereof, are effective and should be included in efficient and translatable interventions. The **objective of this proposal** is to **identify behavioral change strategies that elicit increased PA, sustained for 12 months and, in turn, lead to a reduction in falls and improved QOL**. Building on prior research, the proposed study will use a factorial experimental design to test the relative influence of behavioral change strategies separated into two components. These components are comprised of distinct sets of behavioral change strategies that represent two different ways of motivating people to take action: interpersonal and intrapersonal, consistent with theories of behavioral change^{16, 22} and lifespan development,⁴⁶ as well as empirical evidence.³³ The components will be combined with core intervention content that includes Otago,¹⁰ an evidence-based fall-reducing PA protocol, and a PA-monitor for self-tracking.

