Fall-reducing PA interventions. In a Cochrane review, Gillespie and colleagues identify fall-reducing PA among the most effective fall prevention interventions, yet few studies describe or evaluate strategies to increase “uptake” of and “adherence” to fall-reducing PA.⁶ The dozens of fall-reducing PA intervention studies conducted over the last several decades have generated substantial knowledge about which PAs work to reduce falls and injuries among older adults, including those with multiple chronic conditions, pain, and frailty.⁹ Meta-analyses show the effects of fall-reducing PA interventions on fall rate ratios range from 0.56 to 0.82.^{6,10,11} One example of an evidence-based program emerging from this literature is the Otago protocol, which is cost-effective when delivered 1:1 in home settings¹² and when delivered in small groups.¹³ Otago and other similar PA protocols include instruction and supervisory strategies, but not content to increase the initiation or maintenance of PA. The few intervention studies that have included such content show conflicting results due, in part, to the use of self-report PA measures.^{9,14} *Future studies need to build upon existing evidence-based, fall-reducing PA protocols by combining them with evidence-based strategies to motivate older adults' PA, and estimate their effects on objectively measured PA (e.g., accelerometer).* Below we identify fundamental building blocks that inform such progress.

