standardized effect size of .20. We also anticipate 15% attrition at 12 months, based on our preliminary studies which showed 7% attrition at 6 months. Considering these assumptions, a sample size of 308 (77 per condition) will enable us to detect small but clinically meaningful main effects of the interpersonal or intrapersonal components as well as their interaction (effect sizes of .20), with 80% power, under a two-tailed hypothesis test at a significance level of .05.⁹⁴ This sample size will also enable us to detect medium to large effects on our secondary outcome of falls (fall rate ratios of .40 to .70), with 80% power, under a two-tailed hypothesis test, at a significance level of .05, which is consistent with prior research that shows Otago PA reduces falls (fall rate ratios 0.56 to 0.79).¹⁰

17.3: DATA INTEGRITY

Data Monitoring. Ongoing quality control procedures will be implemented for data collection, storage and processing. The data manager will conduct monthly monitoring of the study database and generate a report for the PI to review at team meetings. Standing agenda items for these meetings will include participant recruitment and retention, serious adverse events, unexpected adverse events, expected adverse events, protocol deviations, data integrity, and overall study conduct.

CHAPTER 18 – CONFIDENTIALITY

17.4: DATA SECURITY

Data Collection. All data from participants screened for the study will be entered and stored in an electronic study database. Designated research staff will collect and enter required data (written informed consent, responses to interview data) onto electronic study data forms. Screened participants who do not meet study eligibility will have specific screening data entered the study database as this data will be helpful in examining the patient population and feasibility of enrollment criteria and will include gender, age, race and reason for exclusion. All dates will be shifted and other Personal Health Information (PHI)--which in this study includes self-reported medical history, fall risk, and medication regimen--will be removed from the study database upon study completion. All data obtained from this study will be used for research purposes only and will not include data from electronic health records.

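### The 80% power claimed for falls rests on no stated fall rate or dispersion and is set beside Otago's effect, which every arm receives; its .70 end is unsupported

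*Combined protocol and SAP*

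**What the plan says.** Section 17.2 says that 308 participants will "enable us to detect medium to large effects on our secondary outcome of falls (fall rate ratios of .40 to .70), with 80% power", two-tailed at .05, and that this is "consistent with prior research that shows Otago PA reduces falls (fall rate ratios 0.56 to 0.79"). It gives no comparison fall rate and no dispersion. Just before, it says "We also anticipate 15% attrition at 12 months" and sizes the trial for main effects of either component on physical activity (PA), and for their interaction.

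Section 1.1 states the falls hypothesis: "Participants receiving the set of interpersonal behavior change strategies will have clinically meaningful reductions in falls and increases in QOL", 12 months after the intervention, against participants who do not receive those strategies. The same section says "All conditions include an evidence-based physical activity protocol endorsed by Centers for Disease Control and Prevention (CDC"), and section 4.1 identifies that protocol: "The evidence-based Otago protocol guides the core fall-reducing PA content in this study". Table 3 gives Otago the same 40 minutes in every condition.

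The only fall incidence in the documents is in section 2.1: "Every year, 1 in 3 people aged 65 and older falls".

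In section 17.1 the falls analysis is a negative binomial regression for a difference between groups at 12 months, with no factor terms or covariates named. The PA models are full factorial and carry baseline PA. Otherwise a covariate enters only if baseline comparisons across conditions flag it as a confounder.

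**The concern.** A detectable rate ratio for counts depends on the comparison rate and on overdispersion as well as on sample size. With both unstated, the claim cannot be checked or used to interpret a null result. A reader who accepts it will think that a true ratio of .70 would be missed in 20% of such trials.

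The supporting comparison is also for another question. An Otago rate ratio describes exercise against no Otago. Here everyone does Otago, and the randomised factors are behavioural strategies added to it, so Otago's effect says nothing direct about the size of the added effect.

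The covariate rule matters because choosing adjusters by baseline tests in a randomised trial selects on chance imbalance, not on prognosis.

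**Working it through.** **Inputs from the documents.** N = 308, 77 per condition; 15% attrition at 12 months; two-sided .05; power 80%; 1 in 3 falling per year at age 65+.

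**Assumed, because not given.** Dispersion k from 0 (Poisson) to 2; one year of follow-up per person; independent participants; no covariates; 40%, 50% or 60% falling as possible enrichment, since section 9.1 requires age 70+ and at least one fall risk factor.

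**n per factor level.** 308 × 0.85 / 2 = 130.9, so 131 after attrition; 308 / 2 = 154 with none.

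**Formulas.**
- Comparison rate from the proportion p who fall: μ = −ln(1−p) if k = 0, otherwise μ = ((1−p)^(−k) − 1)/k.
- Var(log RR) = (1/μ + 1/(RR·μ) + 2k)/n.
- Power = Φ(|ln RR|/SE − 1.96).
- Rate needed for 80% power: μ = (1 + 1/RR) / (n·(ln RR/2.802)² − 2k).

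**The plan's own figure.** It cannot be reproduced, because μ and k are missing. The nearest match to .70 is about 1 fall per person-year, k = 0 and no attrition, which gives 81%. That drops both the overdispersion implied by the choice of a negative binomial model and the stated 15% attrition.

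**One worked case.** For p = 1/3, k = 1 and n = 131, μ = 0.5. Variance = (2 + 2.857 + 2)/131 = 0.0523, so SE = 0.229. Power at .70 = Φ(0.357/0.229 − 1.96) = Φ(−0.40) = 34%.

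**Full range, main effect, k 0 to 2, n 131 to 154.**

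| Proportion falling (comparison level) | Power at .70 | Ratio detectable with 80% power |
|---|---|---|
| 1 in 3 (documents, general 65+) | 31-44% | 0.48-0.55 |
| 40% (assumed) | 35-53% | 0.52-0.60 |
| 50% (assumed) | 41-66% | 0.55-0.65 |
| 60% (assumed) | 45-78% | 0.58-0.69 |

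At .40, power is 92-97% even if only 1 in 3 fall, so that end is met. At .79, the weak end of the Otago range, it is 16-24% if 1 in 3 fall and 21-37% if half fall.

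**What .70 requires.** For n = 131, n·(ln .70/2.802)² = 2.12 and 1 + 1/.70 = 2.43.
- k = 0: 2.43/2.12 = 1.14 falls/yr (68% falling). With n = 154: 0.97 (62%).
- k = 0.5: 2.43/1.12 = 2.16 falls/yr (77% falling). With n = 154: 1.62 (70%).
- No rate is high enough once 2k reaches 2.12, that is k = 1.06. With n = 154 the limit is k = 1.25.

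**Fall-history covariate.** Assume half have a past-year fall, a prognostic rate ratio of 2 to 3, marginal k 0.5 to 1.0 and 0.5 to 1.5 falls/yr. The between-stratum variation (squared coefficient of variation 0.111 at ratio 2, 0.25 at ratio 3) then moves out of the dispersion: conditional k = (k − cv²)/(1 + cv²). Summing the information over the two strata raises power at .70 by 1.1 to 9.1 points.

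**The case against.** **The contrast and time frame are not really missing.** This stands. The preceding sentence in 17.2 concerns component main effects and their interaction, section 1.1 fixes the falls comparison, and both 1.1 and 17.1 give the 12-month horizon. What is missing is the fall rate and the dispersion.

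**The 1 in 3 figure is not this population.** Also true. Participants are 70 or older with a fall risk factor, so more may fall. The 50% and 60% rows allow for that. At 60% with k = 0 and no attrition the detectable ratio is 0.69, close to the stated .70.

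**A reader might infer that .70 is wrong, or that it fails even at 60% falling.** The documents do not support either. A high rate with little overdispersion reaches 80%. The 60% row is for the unadjusted model only: with fall history adjusted at prognostic ratio 3, k = 0.25 and 154 per level, power is 82%. That is a favourable corner, but it exists.

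**A reader might infer that the falls model will use reference coding and so lose power.** Nothing in the plan chooses that. The wording about a difference between groups is loose, and the absence of a stated coding or time offset is missing detail, not a demonstrated fault.

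**The Otago clause is a plausibility remark, not an input.** Fair, and the ranges overlap from 0.56 to 0.70. It is still the only support offered for the falls claim, and it concerns a contrast that this trial does not randomise.

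**The covariate gain is small and falls are secondary.** Both are true. The case for naming the covariate is mainly pre-specification.

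**Conclusion.** The concern holds in limited form. The .40 end is supported for a component main effect. The .70 end is unsupported by anything stated, and the Otago comparison does not supply the support.

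Under the assumptions above, a true .70 would be missed in about 56-69% of trials if 1 in 3 fall, 34-59% if half fall and 22-55% if 60% fall. These figures treat participants as independent. Delivery in groups of 4-6 (section 5.1) could lower power further and is not included.

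This affects how a falls result is read and how its model is specified. A reader might infer that the trial should be larger. That does not follow, because N is set by the PA outcome and falls are secondary.

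**What to change.** (a) In section 17.2, restate the falls sensitivity for the component main effect, as the ratio detectable with 80% power across a stated range of fall rate and dispersion, after 15% attrition. Either allow for correlation within small groups or say that it is ignored. Delete the Otago comparison, or label it as a contrast not tested in this trial.

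(b) In section 17.1, fit the negative binomial falls model with the two component factors, as for PA and quality of life. Pre-specify past-year fall history (any versus none) as a covariate, in place of selection by baseline tests.

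The cost is wording. Past-year falling is already a screening item (section 9.1). It will vary among participants, because unsteadiness or worry about falling can also meet the risk criterion. N and the primary analysis are unchanged. The downside is that the stated falls sensitivity becomes less favourable.
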